6.3.1 Inclusion criteria

A patient must fulfill the following criteria in order to be included in the study:

1. Male and female HLH patients of any age.
2. Patients diagnosed with confirmed or suspected pHLH, based on; a molecular diagnosis or familial history consistent with pHLH or fulfilment of HLH-2004 diagnostic criteria, i.e., five out of eight of the criteria below:

- Fever
 - Splenomegaly
 - Cytopenias affecting 2 of 3 lineages in the peripheral blood (hemoglobin <90 g/L; platelets <100 x 10⁹/L; neutrophils <1 x 10⁹/L)
 - Hypertriglyceridemia (fasting triglycerides ≥3 mmol/L or ≥265 mg/dL) and/or hypofibrinogenemia (≤1.5 g/L)
 - Hemophagocytosis in bone marrow, spleen, or lymph nodes, with no evidence of malignancy.
 - Low or absent NK-cell activity ⁱ
 - Ferritin ≥500 µg/L
 - Soluble CD25 (sCD25; i.e., soluble IL-2 receptor) ≥2400 U/mL ⁱⁱ
3. Presence of active HLH disease as assessed by the investigator.
 4. Patients must fulfil one of the following criteria as assessed by the investigator:
 - Having not responded to previous conventional treatment of HLH
 - Having not achieved a satisfactory response to previous conventional treatment of HLH or worsened
 - Having reactivated ⁱⁱⁱ
 - Showing intolerance to previous conventional treatment of HLH
- At the time of enrollment, eligible patients might still be receiving treatment (induction or maintenance) or might have already discontinued it.
5. Expectation of survival beyond 1 week as judged by the investigator.
 6. Patient has expectation of proceeding to HSCT
 7. Informed consent signed by the patient (as required by local law), or by the patient's legally authorized representative(s) with the assent of patients who are legally capable of providing it, as applicable.
 8. Willing to use highly effective methods of contraception from study drug initiation to 6 months after the last dose of study drug, if female and of childbearing potential.

In case of use of oral contraception women should have been stable on the same brand (or generic equivalent) for a minimum of 3 months before taking study treatment. Women are considered post-menopausal and not of childbearing potential if they have had 12 months of natural (spontaneous) amenorrhea with an appropriate clinical profile (e.g., age appropriate, history of vasomotor symptoms) or have had surgical bilateral oophorectomy (with or without hysterectomy) or tubal ligation at least six weeks ago.

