6.3.5 Specific restrictions/requirements

Females of child-bearing potential require use of highly effective contraceptive measures (failure rate of less than 1% per year) from Screening until 6 months after the last emapalumab treatment have elapsed.

All women who are physiologically capable of becoming pregnant, will have a β -hCG test (serum pregnancy test) performed at screening, baseline and at EOT. Urine pregnancy tests will

be performed monthly during the treatment period and at the scheduled visits day 30, 60, 100, and 6 months after HSCT (or last emapalumab treatment if HSCT is not performed) in the follow-up period.

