6.5 Safety and efficacy assessments

6.5.1 Study schedule

All visits should take place as close to planned dates as possible. Infusions should not take place more than 4 days apart. Detailed information on assessments and timing could be found in Sections 6.5.2 - 6.5.8 and Table 3 and Table 4

In the follow-up period, the following time-windows are allowed:

Pre-conditioning: can be combined with EOT visit provided the two visits are not more than 5 days apart

- Week (W) 1-2-3, Day+30 post-HSCT: ± 2 days
- Day+60, Day+100 post-HSCT: ± 1 week

- 6-months, 1-year post-HSCT: ± 4 weeks

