^o **Chest X-ray:** Chest CT will be accepted as a replacement for Chest X-ray.

^p **Brain MRI:** to be performed in case of CNS disease and/or onset of neurological signs and/or symptoms. Brain CT or cranial ultrasound will be accepted as a replacement of brain MRI.

^q **AE recording:** All AEs are collected from start of the first infusion of study drug, until study completion

^r **SAE recording:** SAEs are collected after signing of ICF until study completion. Thereafter only related SAEs will be reported

^s **Pregnancy test:** Female of childbearing potential will have a serum pregnancy test taken at Screening and Baseline and at EOT and then local urine pregnancy test will be taken monthly (week 4, 8, 12 etc.) until 44 days (corresponding to 2 half-lives) after last emapalumab administration

Table 4 Schedule of events – Follow-up period

Assessments		EOT ^a	Follow-up pre-HSCT ^a	Follow-up post-HSCT (or after last emapalumab infusion, as applicable) ^b					
			Pre-conditioning visit	Weekly visits wk 1 – 2 – 3 ^c	D+30 visit ^c	D+60 visit ^c	D+100 visit ^c	6 months visit ^c	EOS 1 year visit ^c / WD ^d
Clinical Assessments	Vital signs	As indicated in Table 1	X	X	X	X	X	X	X
	Physical Examination ^e		X	X	X	X	X	X	X
	Height								X
	Post-HSCT outcome ^f			X	X	X	X	X	X
	Survival		X	X	X	X	X	X	X
Laboratory	Hematology		X	X	X	X	X	X	X
	Coagulation		X	X	X	X	X	X	X
	Biochemistry		X	X	X	X	X	X	X
	sCD25		X	X	X	X	X	X	X
	Urinalysis		X	X	X	X	X	X	X
Search for infections	TB ^g			X	X	X	X	X	
	Infection search & monitoring	In case of suspicion of infection – according to the patient's clinical presentation							
Imaging	Chest X ray	In case of suspicion of infection							
	Abdominal US ^j	X				X		X	
Concomitant medications		X	X	X	X	X	X	X	
Prophylactic treatment ^m		X	X	X ^m					
AE recording ^k		X	X	X	X	X	X	X	
SAE recording ^l		X	X	X	X	X	X	X	

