6.5.7.1 Pregnancy test

Female of childbearing potential will have a serum pregnancy test taken at screening and Baseline and at EOT and then local urine pregnancy test will be taken monthly (week 4, 8, 12 etc.) until 6 months after the last emapalumab administration.

The outcome of the test will be reported as “positive” or “negative” in the eCRF.

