#### Pregnancy Test

The result of pregnancy test (negative or positive) and type of specimen tested (serum or urine) will be collected for female subjects of childbearing potential. Female subjects of childbearing potential will have a serum pregnancy test taken at screening, visit 1 and EOT visit, and local pregnancy test (urine or blood) will be taken monthly (week 4, 8, 12, etc.) during the treatment period and at day 30, 60, 100 and 6 months after HCST.

A data listing will be provided for pregnancy test results from all scheduled and unscheduled visits.

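### The protocol gives three inconsistent schedules for pregnancy testing after treatment; Table 3 footnote s stops at 44 days, about 139 days before required contraception ends

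*Protocol*

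**What the plan says.** Three places in the protocol set the urine pregnancy tests that follow treatment.

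- Table 3, footnote s (section 6.5.1.1): "local urine pregnancy test will be taken monthly (week 4, 8, 12 etc.) until 44 days (corresponding to 2 half-lives) after last emapalumab administration".
- Section 6.5.7.1: "local urine pregnancy test will be taken monthly (week 4, 8, 12 etc.) until 6 months after the last emapalumab administration".
- Section 6.3.5: urine tests are to "be performed monthly during the treatment period and at the scheduled visits day 30, 60, 100, and 6 months after HSCT". The same sentence counts these visits from the last emapalumab treatment when HSCT is not performed.

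All three agree on serum tests at screening, baseline and EOT. Table 4 covers follow-up and, as the document reads, has neither a pregnancy-test row nor a footnote on it.

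On which source to use, section 6.5.1 says: "Detailed information on assessments and timing could be found in Sections 6.5.2 - 6.5.8 and Table 3 and Table 4". Section 6.5.7.1 lies inside that range, so a site is sent equally to two texts with different stop dates.

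Contraception is required "from study drug initiation to 6 months after the last dose of study drug" (section 6.3.1, criterion 8) and "from Screening until 6 months after the last emapalumab treatment have elapsed" (section 6.3.5). The start differs slightly; the end does not.

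SAP section 6.10.4 describes local tests "monthly (week 4, 8, 12, etc.) during the treatment period and at day 30, 60, 100 and 6 months after HCST", without the alternative for patients who have no HSCT. It plans only a listing of the results.

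**The concern.** Footnote s and section 6.5.7.1 cover the same test, population, frequency and starting point, yet stop at different times. Section 6.3.5 differs from both: it ends monthly testing with treatment, then uses fixed visits counted in the first instance from HSCT. The same conduct can therefore comply with one part of the protocol and deviate from another.

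The footnote matters in practice because Table 4 is silent on pregnancy tests. A coordinator who works from the schedule tables finds footnote s as the only instruction for the period after treatment.

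Two things are at stake. One is detection of pregnancy while contraception is still required; the duty in section 6.5.5.1.6 to report exposure within 24 hours starts only once someone is aware of it. The other is consistent handling of deviations across sites under section 9.4.

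**Working it through.** The plan states no figure to reproduce, so the check sets the rules side by side and counts days.

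**Inputs**

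| Source | Frequency after treatment | Counted from | Stop |
|---|---|---|---|
| Table 3 footnote s | monthly | last dose | 44 days |
| Section 6.5.7.1 | monthly | last dose | 6 months |
| Section 6.3.5 | day 30, 60, 100, 6 months | HSCT; last dose if no HSCT | 6-month visit |
| Contraception (6.3.1, 6.3.5) | – | last dose | 6 months |

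Visit windows from section 6.5.1: day 30 ± 2 days; days 60 and 100 ± 1 week; 6-month visit ± 4 weeks.

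Assumptions: 6 months = 365.25 / 2 = 182.6 days. Monthly tests labelled week 4, 8, 12 are spaced 28 days apart.

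**Step 1. Gap to the end of contraception.** 182.6 − 44 = 138.6, about 139 days.

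**Step 2. Tests under 6.3.5 that footnote s omits, no HSCT.** The tests fall at days 30, 60, 100 and 182.6 after the last dose. Those at 60, 100 and 182.6 lie beyond day 44, so 3 are omitted. The windows do not alter this: the earliest day-60 visit is 60 − 7 = 53, still after 44.

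**Step 3. The same count with HSCT.** Let L be the number of days from last dose to HSCT. The tests fall at L + 30, L + 60, L + 100 and L + 182.6. The last three exceed 44 for every L. The first exceeds 44 only when L > 14.

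- L ≤ 14: 3 tests omitted.
- L > 14: 4 tests omitted.

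With the ± 2-day window, the day-30 visit falls between L + 28 and L + 32. The count is then certainly 3 for L ≤ 12, certainly 4 for L > 16, and either in between. The documents give no typical value of L, so the range is 3 to 4.

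**Step 4. Tests under 6.5.7.1 that footnote s omits.** This rule counts from the last dose whether or not HSCT follows. Days 45 to 182 span 138 days = 4 × 28 + 26. Of the 28 possible positions of a 28-day cycle, 26 give 5 tests and 2 give 4. So 4 to 5 are omitted.

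**Step 5. How many of those monthly tests match planned visits.** Without HSCT, the windows after day 44 are days 53–67, days 93–107, and from day 182.6 − 28 = 154.6 onwards. Over the 28 cycle positions, the number of monthly tests outside every window is 3 in 22 positions, 2 in 5 and 4 in 1. Example: tests at days 28, 56, 84, 112, 140 and 168 leave days 84, 112 and 140 outside. The section 6.3.5 tests all fall on planned visits.

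**The case against.** The strongest reply is that little follows from the conflict. A site that tests to the longest rule satisfies all three. The contraception end date is stated consistently, the serum test at EOT is common to every version, and the 24-hour reporting duty stands whatever footnote s says. The study plans 10 to 18 patients, section 6.2 expects them to be young, and the SAP only lists the results. All of that stands and keeps the priority low. It does not remove the conflict, because nothing tells a site to take the longest rule.

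A second reply is that Table 3 covers the treatment period only. That does not stand: footnote s itself sets a stop date after treatment.

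A third is that counts without HSCT describe the less expected course. Criterion 6 requires an expectation of proceeding to HSCT, and section 6.2 expects most patients to do so. That is a fair point, and it is why the count with HSCT is given separately.

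Three stronger readings are tempting, and the documents do not support them.

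- A reader might infer that sections 6.5.7.1 and 6.3.5 agree on one 6-month rule and only the footnote is out of line. They differ in frequency and, for patients with HSCT, in the point they count from.
- A reader might infer that the last test must fall no earlier than 6 months after the last dose, and so fault the window "6-months, 1-year post-HSCT: ± 4 weeks", which allows about day 155 (182.6 − 28 = 154.6) without HSCT. No document sets such a rule. A visit inside the window complies with section 6.3.5, and a 28-day cycle under section 6.5.7.1 can itself end at day 168.
- A reader might infer that the SAP contradicts section 6.3.5. It gives the same visit days in shortened form, and it does not govern site conduct.

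**Conclusion.** The protocol contains three inconsistent schedules for pregnancy testing after treatment, with no stated precedence and no row in Table 4 to settle the matter. A site following footnote s stops about 139 days before required contraception ends. Against section 6.3.5 it omits 3 tests without HSCT and 3 or 4 with HSCT; against section 6.5.7.1 it omits 4 to 5.

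These counts rest on 6 months taken as 182.6 days, monthly taken as 28 days, and an unknown interval from last dose to HSCT. The number of females of childbearing potential is not given; the group is small and may be empty. The consequence is limited to safety monitoring and consistent deviation handling. No endpoint, estimand or estimate changes. It is a correction worth making because it is specific and cheap, not because the trial's conclusions depend on it.

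**What to change.** 1. Delete the 44-day limit from Table 3 footnote s.
2. Make the section 6.3.5 schedule the single rule, and state it in footnote s and section 6.5.7.1: monthly on treatment, then day 30, 60, 100 and 6 months after HSCT, or after the last dose if HSCT is not performed.
3. Add a pregnancy-test row to Table 4 at those four visits.
4. Optional tidying: add the no-HSCT alternative to SAP section 6.10.4.

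The cost is wording in one footnote and one section, one table row, and a notice to sites. Compared with footnote s, each female of childbearing potential has 3 urine tests after day 44 without HSCT, or 3 to 4 with it, all at visits already planned.

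The choice gives up the monthly frequency of section 6.5.7.1 after treatment. Keeping that frequency to 6 months would also resolve the conflict, but it means 4 to 5 tests after day 44. Without HSCT, 2 to 4 of them, usually 3, would need contacts outside planned visit windows.

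If follow-up is already advanced, a written clarification to sites and one stated rule for classifying past deviations would serve the same purpose.

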6.5.1.2 Screening

Patients will be screened for eligibility prior to enrollment into the study.

A signed informed consent form must be obtained from the patient/patient's legally authorized representative prior to any study specific activities. If applicable assent will be obtained in accordance with local requirements. Once the informed consent is signed the patient will be assigned a patient number.

A pre-screening checklist is an additional tool that is made available to assist the Investigator to make decisions. This checklist enables rapid preliminary assessment of patient's eligibility based strictly on the information available from routine patient care. The pre-screening checklist will be kept at site and will not be shared with Sponsor.

A screening log will be maintained by the Investigator with specification of reasons for non-eligibility.

Any SAE that occurs after informed consent has been signed must be reported.

Screening evaluations should be completed within the 2 weeks prior to the first administration of study drug (Visit 1). Evaluations performed before ICF signature as per routine care, will be accepted for study purposes. Patient's medical record should clearly denote these evaluations as standard of care.

6.5.1.3 Treatment period

Patients will be in the treating unit the day before the first administration of emapalumab SD-1.

During the treatment period, visits for infusion and safety /efficacy assessments will occur on SD0, and twice-a-week thereafter (not more than 4 days apart). After the patient's clinical condition is stabilized, decrease the dose to the previous level to maintain clinical response.

Given the unpredictable course of the disease, in case of reactivation (e.g. triggered by intercurrent infections), subsequent dose increases to 3 mg/kg (and up to 6 or 10 mg/kg, as appropriate) may need to be considered and will be guided by the same clinical and laboratory parameters described above and based on the Investigator's decision.

Treatment period will last until pre-conditioning for HSCT.

An end of treatment (EOT) visit has to be performed 3±1 days after last emapalumab infusion.

6.5.1.4 Follow-up period

After treatment completion or treatment discontinuation (for any reason), patients will continue in the study for long-term follow-up until 1 year after either HSCT or last emapalumab infusion (if HSCT is not performed). This will represent the last visit in the study. If search for a donor is longer than 6 months, the follow-up period will be reduced, and the EOS will take place no later than 18 months after the first dose of emapalumab.

A patient who experiences HLH reactivation during the follow-up period, may be re-treated with emapalumab.

After the patient has completed the EOS visit, they should be treated and followed-up according to investigator judgment and local practice. No further investigational medicinal product will be provided.

In case of an ongoing SAE, the patient will continue to be monitored until resolution or until the outcome of the event is known and stable, beyond the defined study end as necessary.

6.5.1.5 Unscheduled visits

Unplanned visits may occur anytime during the study should the patient need to be assessed or treated for any clinical condition that arises during the study. This includes the evaluation and follow-up of AEs and SAEs. Data collected during such a visit should be entered in the eCRF. An unscheduled visit should not affect the regular visit schedule and assessments.

6.5.2 Medical history

Medical history will be collected during the screening period up until the day of the first dose.

Relevant medical history events with onset date at any time prior to ICF signature date will be recorded in the eCRF.

HLH history will be recorded to the best possible extent, including (as available): molecular diagnosis of HLH and perforin expression and other functional tests performed for the diagnosis of HLH, disease features at diagnosis, date of diagnosis, family history of HLH, conventional treatments received to date, including procedures (such as plasmapheresis and HSCT), molecular diagnosis (genetic and functional test results), EBV load at diagnosis.

If results of genetic and/or functional tests are pending at inclusion, they shall be reported when they become available.

6.5.3 Demography

Date of birth, gender, race, and childbearing potential will be collected at screening.

6.5.4 Efficacy endpoints assessments

6.5.4.1 Overall Response

Overall Response is defined as achievement of either Complete or Partial Response or HLH Improvement, at EOT or week 8 (whichever occurs earlier).

Complete response, partial response and HLH improvement and time to first response will be assessed after the database lock via a programmed algorithm, based on the Table 5 below.

Table 5 Definition of response

Overall Response	
Complete Response	Complete Response is adjudicated if:

	
 - No fever = body temperature <37.5°C - Normal spleen size - No cytopenia = Absolute Neutrophil Counts $\geq 1.0 \times 10^9/L$ and platelet count $\geq 100 \times 10^9/L$ [absence of G-CSF and transfusion support must be documented for at least 4 days to report no cytopenia] - No hyperferritinemia = serum level is <2000 µg/L - No evidence of coagulopathy, i.e., normal D-Dimer and/or normal (>150 mg/dL) fibrinogen levels - No neurological and CSF abnormalities attributed to HLH - No sustained worsening of sCD25 (as indicated by at least two consecutive measurements that are > 2-fold higher than baseline)
Partial Response	
Partial Response is adjudicated if:
 
 - At least 3 of the HLH clinical and laboratory abnormalities (including CNS abnormalities) meet the above-mentioned criteria for "Complete Response" - In the case of "reactivated patients" who enter the study with 3 abnormal HLH features, Partial Response is adjudicated if at least 2 parameters normalize - In case of reactivated patients who enter the study with 2 abnormal HLH clinical and laboratory parameters only, Partial Response is adjudicated if one of the 2 parameters normalizes - There is no progression of other aspects of HLH disease pathology
HLH improvement	
 - Improvement (>50% change from baseline or normalization) of at least 3 HLH clinical and laboratory abnormalities (including CNS abnormalities). - In the case of "reactivated patients" who enter the study with only 2 abnormal HLH features, a change from baseline greater than 50% for both will define HLH as improved.

6.5.4.2 Time to first Overall Response

Time to first response will be assessed after the database lock via a programmed algorithm, based on the Table 5

6.5.4.3 Duration of response

Duration of Response, i.e., maintenance of the response achieved will be assessed after the database lock via a programmed algorithm, based on the Table 5

6.5.4.4 Glucocorticoids tapering

Reduction of glucocorticoids by 50 % or more of the baseline dose

6.5.4.5 HSCT

Information about conditioning for HSCT and of the HSCT will be recorded in the eCRF. This information will be used to calculate the number and proportion of patients able to commence conditioning for HSCT

6.5.4.6 Investigator's assessment of clinical response

Investigator's assessment of clinical response will be collected at every visit throughout the treatment period and will be based on the evaluation of clinical signs and laboratory parameters which characterize the disease; clinical signs, e.g. fever, splenomegaly, CNS symptoms, and laboratory parameters, e.g. CBC, fibrinogen, ferritin, sCD25 levels. The assessment will be assisted by the Investigator's clinical judgment and previous experience in treating patients with pHLH and will be used to assess the achievement of response. The patient's clinical response will be rated as 'complete response', 'partial response', or 'no response' as judged by the investigator

6.5.5 Safety assessments

6.5.5.1 Adverse events

6.5.5.1.1 Definitions

Adverse event (AE)

An AE is any untoward medical occurrence in a patient or study patient administered a pharmaceutical product; the event does not necessarily have a causal relationship with the treatment or usage.

AEs include the following:

- Abnormal test findings, as specified below.
- Clinically significant signs and symptoms.
- Changes in physical examination findings.
- Progression/worsening of underlying disease.

In addition, signs and symptoms resulting from the following should also be handled according to the same principles as AEs:

- Overdose.
- Withdrawal of treatment.
- Interactions.
- Abuse.
- Misuse.

For pregnancies and breastfeeding, see 6.5.5.1.6

Abnormal test findings

An abnormal test finding, e.g. abnormal laboratory analysis results, vital signs, or ECG, should be recorded as an AE in any of the following situations:

- The investigator considers the abnormal test finding to be clinically significant.
- The abnormal test finding is associated with accompanying symptoms. Note, that the symptom, not the test result, should be recorded as an AE.
- The abnormal test finding leads to a medical/surgical intervention including withdrawal of IMP(s) or discontinuation from the study. Repeat/confirmatory testing is not considered a medical intervention.

Preexisting conditions

A preexisting condition (i.e., a disorder present before the AE reporting period started and noted on the pretreatment medical history/physical examination form) should not be reported as an AE unless the condition worsens, or episodes increase in frequency during the AE reporting period.

Procedures

Diagnostic and therapeutic non-invasive and invasive procedures, such as surgery, should not be reported as AEs. However, the medical condition for which the procedure was performed should be reported if it meets the definition of an AE. For example, an acute appendicitis that begins during the AE reporting period should be reported as the AE and the resulting appendectomy entered in the comments section of the eCRF.

Lack of efficacy

“Lack of efficacy” or “expected pharmacological effect has not been reached” will not be reported as an AE or SAE. However, failure of pharmacologic action or therapeutic benefit shall be recorded as an AE when they associated with a SAE or Serious outcome.

Serious adverse event (SAE)

An AE that meets one or more of the following criteria/outcomes is classified as serious:

- Results in death.
- Is life-threatening (i.e., at immediate risk of death).
- Requires in-patient hospitalization or prolongation of existing hospitalization.
- Results in persistent or significant disability/incapacity.
- Is a congenital anomaly/birth defect (i.e., in an offspring to the study patient).
- Is a medically important AE.

Medically important AEs are events that may not result in death, be life threatening, or require hospitalization but may be considered serious when, based upon appropriate medical judgment, may jeopardize the patient, or patient or may require medical or surgical intervention to prevent one of the outcomes listed above. Examples of such events are intensive treatment in an emergency room or at home for allergic bronchospasm, blood dyscrasias or convulsions that do not result in hospitalization or development of dependency or abuse.

Serious also includes any other event that the investigator or company judges to be serious. Any suspected transmission of an infectious agent via IMP shall also be considered serious.

Hospitalization

Hospitalization includes transfers within a hospital (e.g. from the psychiatric unit to the intensive care unit) and also includes admissions less than 24 hours. The following situations are not considered hospitalizations (although other SAE criteria may still apply):

- Outpatient procedures / ambulatory care.
- Emergency department visits.

Hospitalization in the absence of an AE occurring during the study should not be considered an SAE. This includes:

- Hospitalization due to a pre-existing condition not associated with a worsening of the pre-existing condition.
- Protocol specified admission.
- Elective admission, e.g. due to cosmetic surgery.
- Pre-planned admission for a condition specified at baseline for the patient.

[figure not shown]
Suspected Unexpected Serious Adverse Reaction (SUSAR)

A SUSAR is an unexpected serious adverse event, suspected to be related to the study drug, which is not consistent with the reference safety information in the Investigator's Brochure.

